#### Potential Risks of No Treatment

Since Omegaven™ will only be offered to those patients for whom no standard therapy is likely to be safe and effective, the risks of not being treated are those allowing for the natural history of their disease and associated clinical manifestations to progress. These include fulminate liver failure and death.

#### Summary – Overall Risk Assessment

Patients will be at some risk inherent in taking a pharmaceutical agent that has not been fully evaluated for long duration treatment. However, the availability of safety data demonstrates no life-threatening risks or toxicities to vital organs or physiologic functions. Prolonged bleeding times and inhibition of platelet aggregation are a potential risk, especially to those patients with an underlying coagulopathy or those being treated with an anticoagulant. The potential benefits of Omegaven™ in this patient population are mainly based on the experimental evidence and a single case of dramatic success. However, the study will only be available to those for whom no standard therapy is available or appropriate, or has already failed. The risks and potential benefits will require careful individual assessment by both the investigators and patients. The heterogeneity of clinical manifestations will lead to non-uniform risk-benefit ratios across the eligible patient population.

## **8.0 Reporting of Adverse Events or Unanticipated Problems involving Risk to Participants or Others**

Adverse events (AEs) will be assessed and reported from the time of the first Omegaven™ infusion until exit from the study. In particular, the patient will be observed during and shortly after Omegaven™ administration for the occurrence of anaphylactic or allergic reactions. Other expected adverse events include death, blood stream infection; hemodynamic instability; re-hospitalization for treatment of blood stream infection, dehydration, electrolyte abnormalities, catheter malfunctions, bowel obstructions, and

urinary tract infection. Unexpected adverse events will also be assessed and reported in compliance with the VUMC IRB requirements. Patients experiencing any adverse events that are moderate or severe in nature and that may be related to Omegaven™ will have their treatment temporarily halted until the adverse event has resolved. Dose modifications will occur as described above. If a dose reduction is made for adverse events later considered to be unrelated to Omegaven™, the Omegaven™ dose will be increased back to the dose prescribed prior to the dose reduction. Patients with anaphylactic or allergic reactions will not continue Omegaven™ treatment.

Any serious or unsuspected adverse events will be reported to the VUMC IRB and the FDA within 72 hours of the occurrence being known, or within 24 hours if the event is fatal or life threatening. This will be done in person, by telephone, or email, and by completion of the IRB form for adverse/unexpected event reporting.

Adverse events are detected by VCH Neonatology medical and nursing staff during provision of standard care services including the routine monitoring of vital signs and daily physical exam data. Adverse events identified by VCH NICU staff are reported to the Principal Investigator immediately by telephone or pager, and subsequently to the appropriate board or committee.

The PI, [name], will be responsible for assuring that adverse event reporting requirements are actually met. Any patients who have agreed to participate in the trial, but who have not yet undergone intervention, will be informed of adverse events. A revised consent document will be submitted to the IRB with the adverse event form for review and approval. All adverse events will be classified by the Principal Investigator as definitely, probably, possibly, or unrelated to administration of study drug.

## **9.0 Study Withdrawal/Discontinuation**

Patients will be withdrawn from the study for any of the following:

- a) Toxicity considered unacceptable by the Principal Investigator
- b) Patient/guardian requests to discontinue treatment and/or observation for any reason.
- c) A suitable organ has been located and the patient is able to undergo a liver or liver/intestinal transplant.
- d) Decision by the Principal Investigator that termination is in the patient's best medical interest.

In the event that a patient is withdrawn from the protocol, study staff will document the date of withdrawal, the reason for withdrawal, and the results of all measurements of interest made up to date of withdrawal.

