#### Discontinuation of Therapy

Patients will continue to be followed by the PI if in-patient or if discharged they will be followed in the Out-Patient GI Clinic upon discontinuation of therapy with Omegaven™ for a minimum of 2 months after the treatment is stopped.

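### Sections 8.0 and 9.0 require data only to withdrawal or an undefined study exit, while Section 6.0 promises at least 2 months of follow-up after treatment stops

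*Combined protocol and SAP*

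**What the plan says.** Section 9.0 lists four reasons for withdrawal from the study. Reason (a) is toxicity that the investigator finds unacceptable, (c) is a transplant that has become possible, and (d) is the investigator's judgement that stopping serves the patient best. Reason (b) reads "Patient/guardian requests to discontinue treatment and/or observation for any reason".

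For a withdrawn patient, staff note when and why the patient left, together with "the results of all measurements of interest made up to date of withdrawal". Nothing is specified for the time after that date.

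Under Section 8.0, adverse events "will be assessed and reported from the time of the first Omegaven™ infusion until exit from the study". Exit is not defined.

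In Section 6.0, Discontinuation of Therapy says patients are followed "for a minimum of 2 months after the treatment is stopped". It makes no exception by reason for stopping and does not list the data to be collected. Section 6.0 also lets the clinical team remove a patient from the protocol when calorie intake is inadequate, again without a data rule.

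Section 10.0 plans to collect transplant, mortality and transfusion events, with no time window. The time-to-normalization result is to be compared with an analysis leaving out patients who die or are transplanted. One version of the trend models gives those patients the worst possible value after the event.

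**The concern.** Section 9.0 makes no distinction between stopping the drug and leaving observation. Even a family that wants only to stop treatment falls under study withdrawal, because reason (b) joins the two. Staff could follow Sections 8.0 and 9.0 to the letter and record nothing about a patient after withdrawal, although Section 6.0 says that patient is still being seen.

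Reasons (a), (c) and (d) bear on safety or prognosis, so data missing after such withdrawals would plausibly be informative. Safety is Aim 1, and Hypothesis 2.4 concerns transplant, death from hepatic causes and transfusion. The bilirubin endpoint is exposed too: it needs three consecutive values below 2 mg/dL, so a withdrawal partway through that run leaves the outcome undetermined.

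**Working it through.** The plan states no sample size, dropout rate or expected event count, so there is no figure of its own to reproduce. The check is a comparison of the sections, followed by two illustrations of scale.

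**The sections side by side**

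| Route out | Recorded at withdrawal | Required afterwards by 8.0 and 9.0 | Analysis rule in 10.0 |
|---|---|---|---|
| (a) Toxicity | Date, reason, results to date | Nothing stated | None |
| (b) Family request, treatment only | Same | Nothing stated | None |
| (c) Transplant | Same | Nothing stated | Worst value in one version of the trend models; comparison excluding transplanted patients |
| (d) Investigator decision | Same | Nothing stated | None |
| Removal for inadequate calories (6.0) | No data rule | Nothing stated | None |

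Section 6.0 promises at least 2 months of follow-up to anyone who stops treatment. No sentence says whether a Section 9.0 withdrawal receives it, or whether study exit falls at withdrawal or at the end of that follow-up. Suppose an infant withdrawn for toxicity dies two weeks later. Section 9.0 does not ask for the death. Section 10.0 says mortality is collected, but not until when. If the death is not known, neither the worst-value rule nor the comparison excluding deaths can be applied correctly.

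**Illustration 1: weight of missed events**

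Input: n = 13, the count in the anemia note in Section 7.0. It is the only patient count for this study and is not a planned size. Let k be the patients withdrawn without normalizing, and assume everyone else normalizes.

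- Share whose later events could go unseen, k/13: 7.7%, 15.4%, 23.1% and 30.8% for k = 1, 2, 3 and 4.
- Proportion normalized if withdrawn patients are dropped: 100%.
- Proportion normalized if they count as failures, (13 − k)/13: 92.3%, 84.6%, 76.9% and 69.2%.

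**Illustration 2: time to normalization**

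Assume constant hazards over one fixed period. Let F be the probability of normalization if withdrawal could not occur, and W the probability of withdrawal if normalization could not occur. Both are assumptions. Censoring withdrawals as uninformative estimates F. Treating withdrawn patients as never normalizing gives

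CIF = L1/(L1 + L2) × (1 − exp(−(L1 + L2))), with L1 = −ln(1 − F) and L2 = −ln(1 − W).

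For F = 0.50 and W = 0.20: L1 = 0.693, L2 = 0.223, and CIF = 0.756 × 0.600 = 0.454.

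| F | W = 10% | W = 20% | W = 30% |
|---|---|---|---|
| 50% | 47.7% | 45.4% | 42.9% |
| 70% | 67.1% | 64.1% | 60.9% |

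The gap runs from 50 − 47.7 = 2.3 points to 70 − 60.9 = 9.1 points. That is one extreme. If withdrawn patients would have normalized at the same rate as the rest, censoring them gives no bias; if faster, the sign reverses.

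**The case against.** The strongest reply is that no section says collection ends. Section 9.0 sets out what must be documented when a patient is withdrawn and does not forbid recording more. If exit means the end of the Section 6.0 follow-up, Sections 6.0 and 8.0 agree. Section 8.0 also takes patients with allergic reactions off the drug without calling this study withdrawal. The procedure calendar, Appendix A, is listed in the contents but is not in the text reviewed, and it may settle the matter. This stands in part: the end of collection is a permitted reading, not a stated rule. The defect is that nothing in the available text excludes it.

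A reader might infer that the worst outcomes are lost. The documents do not support that. The toxicity or transplant that triggers withdrawal is recorded as the reason, and Section 10.0 plans to collect transplant and mortality. What is at risk is narrower: events and bilirubin after withdrawal, mainly under (a) and (d), and deaths and adverse events after a transplant.

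A third objection concerns the remedy. After a transplant, bilirubin reflects a new liver, so it should not be used as an efficacy outcome. For patients who return to conventional emulsion, bilirubin after the drug stops answers a different question from bilirubin on the drug. Both points are right. They limit what should be collected and require the analysis to say which question it answers, but they do not justify leaving these patients without a rule.

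**Conclusion.** The point holds as an unreconciled conflict with a consequence for the data. Sections 8.0 and 9.0 permit loss of safety and bilirubin data after withdrawal for reasons related to safety or prognosis, against the follow-up promised in Section 6.0. Section 10.0 covers death and transplant only in part and leaves toxicity and investigator-decision withdrawals without a rule.

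For counts of deaths, bleeds, infections and other adverse events, missed events can only lower the observed Omegaven figure. A reader might infer that every resulting bias favours Omegaven. That does not follow for time to normalization: no censoring rule is stated, and late normalizations could be missed as well. For comparisons with soybean emulsion, the direction also depends on comparator follow-up, which is not described.

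The size cannot be established. The 7.7 points per missed event and the 2 to 9 points for normalization rest on a count that is not a planned sample size and on assumed probabilities; the documents report no withdrawal and no later event. The change should be made, but it does not undermine the study as a whole.

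**What to change.** Reconcile Sections 6.0, 8.0 and 9.0:

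1. Separate stopping Omegaven from refusing further observation, including within reason (b). Apply the same data rule to removals under Section 6.0.
2. Define exit from the study as the end of the Section 6.0 follow-up or refusal of observation, whichever comes first.
3. Unless observation is refused, collect adverse events, vital status and transplant through that follow-up, and bilirubin up to any transplant.
4. In Section 10.0, treat death and transplant as competing events in the time-to-normalization analysis. Keep other patients who stop the drug under observation, and state that their later values may come after a return to conventional emulsion. Add a sensitivity analysis counting these patients as not normalized.

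The cost is wording in these sections and some extra chart abstraction, since the follow-up visits are already promised. No change to any clinical stopping rule is proposed.

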## **10.0 Statistical Considerations**

### ***Analysis of Safety and Tolerability of Omegaven™***

All primary safety and tolerability analyses will be based on descriptive statistics. In secondary analyses, we will also assess the statistical significance of differences. Some safety and tolerability outcomes will be measured only in the Omegaven™ group. For those, we will compare results before starting PN with Omegaven™ (while receiving PN with soybean oil fat emulsions) with after starting PN with Omegaven™. The period receiving Omegaven™ will start to be counted 30 days after beginning PN with Omegaven™ for the main analysis.

Primary outcomes measured in the Omegaven™ group will include routine measurement of the direct bilirubin levels and whether the INR was ever  $> 2$ .

Primary outcomes measured in the Omegaven™ and soybean based fat emulsion groups will include whether triglycerides were ever  $> 400\text{mg/dL}$ , whether albumin was ever  $> 3$ , any occurrence of unexpected bleeding and number of times it occurred, occurrence of any anaphylactic reaction, rate of blood stream infections as shown by positive blood cultures, rate of line infections and gram positive central venous catheter infections..

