#### Hypothesis for Aim 1:

1.1 – PN containing Omegaven™ will be safe for patients with respect to the risk of unexpected bleeding, coagulopathies, and other adverse events.

1.2 – PN containing Omegaven™ will promote more short-term growth and development than conventional fat emulsions.

1.3-Incidence of sepsis will be similar to historical incidence of sepsis on TPN and IL™

2. To determine if established PN associated liver disease can be reversed or its progression halted by using a parenteral fat emulsion prepared from fish oil as measured by normalization of serum levels of hepatic enzymes and bilirubin.

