## 7.0 Risks

## Potential Risk of Omegaven™ Treatment

Omegaven has been studied in animal pre-clinical models as well as Phase I, II, III, and post marketing human trials in both Europe and Asia. Prolonged bleeding time and an inhibited platelet aggregation can occur. It should not be administered to patients known to be allergic to fish or egg protein.

Contraindications to Omegaven™ include the following:

- Impaired lipid metabolism
- Severe hemorrhagic disorders
- Unstable diabetes mellitus
- Collapse and shock
- Stroke/Embolism
- Recent cardiac infarction
- Undefined coma status

Side effects:

The infusion of Omegaven™ can lead to a prolonged bleeding time and an inhibited platelet aggregation. In rare cases, patients may experience a fishy taste.

The administration of Omegaven™ should be stopped or reduced if there is a marked increased in blood glucose levels during the Omegaven™ infusion. Undesirable effects that are seen during the infusion of Omegaven™ that may also occur with conventional fat emulsions (i.e., Intralipid®) include:

- Slight rise in body temperature
- Heat sensation and/or cold sensation
- Chills
- Flushing or cyanosis
- Lack of appetite, nausea, vomiting
- Dyspnea
- Headache, pain in the chest, bone pain
- Priapism
- Increase/decrease blood pressure
- Anaphylactic reactions/erythema

A recent review of the literature suggests a slight change in risk status. There was a single case report of an infant developing anemia : [J Pediatr.](#) 2010 Feb;156(2):324-6.e1, Parenteral fish oil-associated burr cell anemia. [Mallah HS](#), [Brown MR](#), [Rossi TM](#), [Block RC](#). The mechanisms responsible for formation of burr cells are unknown but have been attributed to changes in composition of the lipids of the red blood cell membrane. These changes affect erythrocyte fragility and ultimately cause shape alterations, which make the red blood cells more susceptible to trapping and destruction by the spleen. None of the 13 infants in our study has developed any anemia and we will now monitor for that reported complication.

Other expected adverse events that are common to all patients with short bowel syndrome, regardless of the type of fat emulsion they receive, include blood stream infections and re-admittance to hospital. Causes for re-hospitalization include dehydration, bloodstream infections, electrolyte abnormalities, bowel obstruction, and central venous catheter malfunction.

Overdose:

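### Hypothesis 1.1 claims that Omegaven is safe, but descriptive counts and significance tests do not show how much harm the data leave possible; exact intervals would

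*Combined protocol and SAP*

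**What the plan says.** Aim 1 in Section 2.0 is to determine the safety profile. Its first hypothesis is an assertion: parenteral nutrition with Omegaven "will be safe for patients with respect to the risk of unexpected bleeding, coagulopathies, and other adverse events".

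Section 10.0, on safety and tolerability, gives the analysis: "All primary safety and tolerability analyses will be based on descriptive statistics". It continues: "In secondary analyses, we will also assess the statistical significance of differences". The outcomes are largely ever/never events. For the Omegaven group alone: "Primary outcomes measured in the Omegaven™ group will include routine measurement of the direct bilirubin levels and whether the INR was ever" above 2, with a comparison before and after the switch in the same infants. For both the Omegaven and soybean groups, the list includes triglycerides ever above 400 mg/dL and "any occurrence of unexpected bleeding and number of times it occurred, occurrence of any anaphylactic reaction".

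The same section starts the Omegaven period at day 30 for the main analysis, whereas Section 8.0 collects adverse events from the first infusion.

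Section 7.0, after citing a case report of burr cell anemia, says: "None of the 13 infants in our study has developed any anemia and we will now monitor for that reported complication".

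The available text states no confidence interval, acceptable event rate, margin, significance level, planned sample size or rule for judging hypothesis 1.1.

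**The concern.** A claim of safety needs a statement of how large a harm the data rule out. The planned output does not give one. A descriptive count reports what was seen, and a test of difference asks whether the data are incompatible with no difference. With few infants and uncommon events, an observed zero and a non-significant test are both likely even when the true risk is appreciable.

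At stake is what can be written about hypothesis 1.1 for bleeding, coagulopathy and anaphylaxis in infants whose underlying disease the protocol calls life threatening. As planned, the analysis yields nothing that can answer the hypothesis in either direction.

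**Working it through.** **Inputs.** The plan has no figure of its own to reproduce: no sample size, power or confidence limit is stated. The only count of infants in this study is 13 (Section 7.0), which is enrolment to date, with zero events, quoted for anemia. All other sample sizes, event rates and comparator sizes below are assumptions.

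**Step 1: what zero events leave possible.** With 0 events in n infants, the exact (Clopper-Pearson) two-sided 95% upper limit is 1 − 0.025^(1/n), and the one-sided 95% limit is 1 − 0.05^(1/n).

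| n (assumed, except 13) | Two-sided 95% upper limit | One-sided 95% upper limit |
|---|---|---|
| 10 | 30.8% | 25.9% |
| 13 | 24.7% | 20.6% |
| 20 | 16.8% | 13.9% |
| 30 | 11.6% | 9.5% |
| 50 | 7.1% | 5.8% |

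For n = 13: 1 − 0.025^(1/13) = 0.247. One event in 13 gives an exact interval of 0.2% to 36.0%.

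**Step 2: how easily a zero arises.** The probability of 0 of 13 is (1 − p)^13. For p = 5% it is 0.95^13 = 0.51; for 10%, 0.90^13 = 0.25; for 20%, 0.80^13 = 0.055.

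**Step 3: how many infants a given bound needs.** Solving (1 − L)^n ≤ 0.025 for zero events gives n = 17, 36 and 72 for two-sided upper limits L of 20%, 10% and 5%.

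**Step 4: what a significance test would detect.** Fisher's exact test at two-sided 0.05, with power by full enumeration, harm direction (true rate 30% on Omegaven, 10% on comparator):

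- 13 v 13: 11.6%
- 13 v 39: 33.7%

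The direction matters. With the rates reversed (Omegaven 10%, comparator 30%), 13 v 39 gives 22.8%, but that is not the harm of interest. In the harm direction, a threefold event rate would still be missed about two times in three or more.

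A single table shows why. With 13 v 13, 4 events against 0 has one-tail probability C(13,4)/C(26,4) = 715/14,950 = 0.048, so the two-sided p is 0.096. It takes 5 against 0 (1,287/65,780 = 0.0196, doubled 0.039) to fall below 0.05.

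**Step 5: the counting window.** If events in the first 30 days are outside the main count, a zero becomes easier to reach, and an interval computed on that window would not cover early events. Section 10.0 does not make clear whether the day-30 start applies to every safety outcome or only to the before/after comparison.

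**The case against.** The strongest case against has four parts.

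- **The design is preliminary.** This is an open-label, non-randomized study of safety and preliminary efficacy. Descriptive safety reporting is normal there, and the plan already makes the tests secondary. That stands as a defence of description. It does not defend pairing description with an assertion of safety and no bound. An exact interval is itself a descriptive statistic, so asking for one does not change the character of the study.
- **No decision rule is stated.** A reader might infer that the plan will declare Omegaven safe on zero events or on p > 0.05. The documents do not say so. Section 7.0 does not use its zero count that way either: it reports a slight change in risk status and adds monitoring.
- **13 is not the analysis set.** A reader might also take 24.7% as the bound this trial will deliver. The figure of 13 is enrolment at one update and refers to anemia, which is not among the listed Section 10.0 outcomes. Some pages were not available, and a planned number may stand there. This objection holds, which is why the limits are shown over a range.
- **Other safeguards exist.** Laboratory monitoring, causality classification, expedited reporting and withdrawal for toxicity protect individual infants. They do not quantify what the cohort can say about hypothesis 1.1.

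**Conclusion.** The concern holds in a limited form. Hypothesis 1.1 asserts safety, while the stated analyses neither bound the harm still possible nor treat non-significance as uninformative. The gap does not depend on 13: for zero events the two-sided exact upper limit runs from 30.8% at 10 infants to 7.1% at 50. Power against a rise from 10% to 30% is 12% with 13 v 13 and 34% with 13 v 39.

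These figures rest on assumed sample sizes, on a zero-event scenario that the plan does not state for bleeding, INR or anaphylaxis, and on assumed event rates and comparator numbers. They illustrate the size of the gap and do not predict the result. The documents do not support the stronger statement that zero events in 13 infants will be taken as proof of safety. The change is worth making because it alters what hypothesis 1.1 can conclude, at the cost of reporting text only.

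**What to change.** In the safety part of Section 10.0:

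1. For the binary harm outcomes (INR ever above 2, triglycerides ever above 400 mg/dL, unexpected bleeding, anaphylaxis), report exact (Clopper-Pearson) 95% intervals. Albumin ever above 3 should stay out of this list, since a high proportion there is not evidently harm.
2. Where both groups are measured, add exact intervals for the between-group difference. For the before/after INR comparison, use a paired method, because the same infants contribute to both periods.
3. For repeat events, such as the number of bleeds and the infections, report rates per patient-time with an interval that allows for clustering within infant. A simple Poisson interval could be too narrow.
4. Use these intervals in place of significance tests as the supporting analysis. Word the 1.1 conclusion as the event rate the data exclude, or recast 1.1 as a descriptive aim.
5. Report the intervals for events from first infusion as well as for the window starting at day 30, so that early events are not left out of the bound.

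Cost: a short edit to Section 10.0 and standard output, with no new data. The drawback is that the safety statement becomes less favourable. With a small cohort the excluded rate will be high, and the report will have to say so.

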## Details of Omegaven™ Administration

After baseline labs are obtained (Table 2 and 3), therapy with Omegaven™ will be initiated at the goal dose of 1 gram /kg/day and is infused over 12-24 hours. Omegaven™ will be infused intravenously through either a central or peripheral catheter alone or in conjunction with parenteral nutrition. If additional fat calories are needed, they will be provided via the enteral route.. The same standards of care provided to all patients receiving parenteral nutrition solution will be followed. Routine nutritional monitoring is described in Table 3.

Table 2: Suggested Schedule Safety Monitoring for Omegaven™ Therapy

(To be done baseline pre-Omegaven™ therapy and weekly until direct bilirubin <0.4 mg/dL)

Parameter	Baseline	Biweekly	Monthly
Essential Fatty Acid Profile	X		X
PT	X	X	
PTT	X	X	
INR	X	X	

Table 3: Suggested Monitoring Schedule for Omegaven™ Therapy  
(Amended December 26, 2006)

Parameter	Baseline (pre- Omegav- en)	Dail y	Q week * -	Periodicall y**
Weight	X	X		
Fluid balance	X	X		
Vital Signs	X	X		
Catheter site/function	X	X		
Laboratory test:				
Sodium	X		X	
Potassium	X		X	
Chloride	X		X	
Glucose	X		X	
BUN	X		X	
Creatinine	X		X	
Triglycerides	X		X	
Calcium	X		X	
Magnesium	X		X	
Phosphorus	X		X	
Prealbumin	X		X	
C reactive protein	X		X	
Albumin	X		X	
Total protein	X		X	
SGPT	X		X	
Alkaline phosphatase	X		X	
Bilirubin (total and direct)	X		X	

GGT	X		X	
AST	X		X	
Copper				X
Iron				X
Vitamins A,D,E				X
Essential Fatty Acid Profile	X		X	
Free cholesterol	X		X	
Free fatty acids	X		X	
Lipid Panel	X		X	
Hemoglobin	X		X	
Hematocrit	X		X	
RBC	X		X	
WBC	X		X	
Platelets	X		X	
PT	X		X	
PTT	X		X	
INR	X		X	
Fibrinogen				
Selenium				X
Zinc				X
Carnitine				X
Aluminum				X
Retinol binding protein (check when getting Vit A)				X

\* More often as necessitated by clinical course; may be reduced in patients who are stable and whose biochemical markers have improved. Refer to protocol for additional information

In the event that a patient is unable to achieve adequate calories parenterally and is unable to tolerate enteral feeds, it may be necessary to evaluate whether or not the patient should continue the study with Omegaven™ as monotherapy or resume therapy with conventional fat emulsions so that additional parenteral fat calories can be given. The clinical team, in conjunction with the patient's primary physician, will determine if the patient should be removed from the protocol. The DSMB will also be notified.

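### The INR and triglyceride safety comparisons are defined on ever-above-cut-off flags, which lose power against the scheduled weekly values; the loss is large if the cohort is small and crossings are rare

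*Combined protocol and SAP*

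**What the plan says.** The safety part of Section 10.0 opens with "All primary safety and tolerability analyses will be based on descriptive statistics". Testing comes second: "In secondary analyses, we will also assess the statistical significance of differences". No test, significance level or power is stated.

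The laboratory outcomes are flags:

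- **INR**, in the Omegaven group only: "whether the INR was ever" above 2. For outcomes measured only in that group, "we will compare results before starting PN with Omegaven™ (while receiving PN with soybean oil fat emulsions) with after starting PN with Omegaven™".
- **Triglycerides**, in the Omegaven and soybean groups: "whether triglycerides were ever" above 400 mg/dL.
- **Albumin**, in both groups: ever above 3, with no unit.

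In Section 6.0, Table 3 ("Suggested Monitoring Schedule for Omegaven™ Therapy") lists all three at baseline and weekly. Table 2 also covers INR; its heading says weekly but its column says biweekly. A footnote to Table 3 lets testing become more or less frequent with the infant's clinical course.

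Under efficacy, Section 10.0 plans longitudinal models of liver function markers and graphs of individual profiles. The markers are not listed.

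**The concern.** Each infant's series of INR or triglyceride values is reduced to one yes/no before any comparison. Values could rise in most infants without anyone passing the cut-off, and the comparison would show nothing. Even a several-fold increase in the number crossing can miss significance when there are few infants.

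For triglycerides the protocol itself may make crossings rarer. Under Dose Modification in Section 6.0, measures are considered once the level exceeds 200 mg/dL, half the outcome cut-off. An upward shift that is managed at that point need never appear as a value above 400.

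Safety is Aim 1, and hypothesis 1.1 names bleeding and coagulopathies. What is at stake is that a non-significant result from a weak test gets taken as reassurance, when the values needed for a better comparison are largely collected anyway.

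**Working it through.** The plan gives no power figure to reproduce, so this check is illustrative.

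**Inputs**

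- Sample size: no planned N is available. The only count is 13 infants to date (Section 7.0). Assumed range: 13 to 50 pairs, or per group.
- Assumed because not stated: two-sided 5% level; exact McNemar (before/after) and Fisher (two groups) for flags; t-tests for values; equal groups; normal values on the analysis scale; shift d = 0.8 SD; before/after correlation r = 0.5.
- Reference proportion ever crossing, p0: assumed 2%, 5% or 10%, with 30% for contrast.

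**Step 1. Crossings needed at N = 13**

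- McNemar, k infants newly crossing and none reverting: p = 2 × 0.5^k. For k = 5, p = 0.0625; for k = 6, p = 0.031. So 6 of 13 (46%) are needed.
- Fisher, 13 v 13, k against 0: p = 2 × C(13,k)/C(26,k). For k = 4, 2 × 715/14,950 = 0.096; for k = 5, 2 × 1,287/65,780 = 0.039. So 5 against 0 are needed.

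**Step 2. What the shift does to the flag**

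p1 = Φ(Φ⁻¹(p0) + 0.8). This takes 2% to 10.5%, 5% to 19.9%, 10% to 31.5% and 30% to 60.9%.

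**Step 3. Power**

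Flag tests: enumerate all outcomes and add the probabilities of those with p ≤ 0.05. Value tests: noncentral t. At N = 13 the noncentrality is:

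- paired, d√n / √(2(1 − r)) = 0.8 × √13 = 2.88 on 12 df, power 75%;
- two groups, d√(n/2) = 0.8 × √6.5 = 2.04 on 24 df, power 50%.

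| Comparison | N | Flag, p0 2% | 5% | 10% | 30% | Values |
|---|---|---|---|---|---|---|
| Before/after (INR) | 13 pairs | 0.1% | 1% | 6% | 20% | 75% |
| | 30 pairs | 5% | 27% | 51% | 73% | 99% |
| | 50 pairs | 24% | 61% | 82% | 95% | >99% |
| Two groups (triglycerides) | 13 each | 0.6% | 5% | 14% | 27% | 50% |
| | 30 each | 5% | 24% | 42% | 59% | 86% |
| | 50 each | 22% | 50% | 70% | 85% | 98% |

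**Step 4. Required size**

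By normal approximation, 80% power in two groups at 0.8 SD needs 2 × (1.96 + 0.84)² / 0.8² = 24.5, so 25 per group, on the values. The flag needs 127, 76, 55 or 40 per group at p0 of 2%, 5%, 10% or 30%.

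**Step 5. Repeated values**

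Simulated two-group comparison, eight values per infant, intraclass correlation 0.5, shift in SDs of a single value, flag against infant mean:

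- 13 per group, 0.5 SD (ever-crossing 10% v 25%): 6% against 39%.
- 13 per group, 1.0 SD (10% v 48%): 43% against 91%.
- 30 per group, 1.0 SD: 86% against nearly 100%.

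The flag test was weaker in every scenario run, but by very different margins.

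**The case against.** **The tests are secondary.** The primary safety analysis is descriptive, and it also covers bleeding, anaphylaxis and infection. A reader might infer that the plan cannot answer its safety question. The documents do not support that: Aim 1 does not rest on these tests, and nowhere does the plan say that a non-significant result will be read as safety. This limits the weight of the point but does not remove it, because the tests are announced without any caution on interpretation.

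**Power cannot be known.** A reader might infer that the tests have almost no power whatever the cohort. That does not hold. Thirteen is a running count, not a planned N, and the table shows flag tests reaching 70–95% with 50 infants and a reference rate of 10% or more. Part of the gap at N = 13 is also the conservatism of the exact test: a mid-p McNemar gives p = 0.031 at five one-way crossings. The plan names no test, so the exact tests are an assumption here.

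**The flags may not be the only analysis.** The safety outcome lists are worded as inclusive. The efficacy models could take in INR or albumin, because their markers are not listed. So it cannot be said that these laboratory values are tested only as flags. The gap is clearest for triglycerides, which are not a natural liver function marker. For INR, a possible place in an efficacy model is not a commitment to a safety comparison.

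**Albumin does not fit.** Its flag is for ever being above 3, and nothing in the documents treats high albumin as a harm. Its direction must be settled before power to detect harm means anything.

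**The data are not all scheduled.** Table 3 provides one value before Omegaven and does not cover a soybean group. Earlier and comparator values would have to come from charts. This stands and is reflected in the fix, but the plan's own before/after and between-group flags need those same values.

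**Conclusion.** The point holds as one about efficiency and interpretation in a secondary analysis. The named INR and triglyceride safety outcomes are flags, weekly values are scheduled, and no safety analysis of those values is committed to.

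The loss is large for 13 to 30 infants with 2–10% crossing in the reference condition. For a 0.8 SD shift the flag tests have about 0–51% power before/after, against 75–99% on the values, and about 1–42% between groups, against 50–86%. It shrinks with larger cohorts or commoner crossings. These figures rest on the assumed N, crossing rates, shift, correlation, normality and exact tests; only the 13 comes from the documents. What does not depend on N is that the flag test was weaker in every scenario examined, and that its non-significance is poor evidence of safety.

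**What to change.** In Section 10.0:

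1. Keep the ever-above-cut-off counts as the descriptive primary safety outcomes.
2. Make the secondary comparisons on the continuous values. For log INR, use a within-infant before/after mixed model. For log triglycerides, use a between-group repeated-measures comparison, adjusted for baseline where available. Report ratios of geometric means with 95% confidence intervals.
3. Use routinely scheduled values in the main analysis, so that extra tests prompted by illness do not distort infant means. Reconcile the INR frequency in Tables 2 and 3 so that scheduled is defined.
4. State that pre-Omegaven and soybean-group values come from medical records.
5. State that a non-significant flag comparison is not evidence of safety.
6. Clarify the unit and direction of the albumin flag, and only then treat albumin the same way.

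The cost is wording, modest extra analysis and chart abstraction that the planned comparisons already require. No new samples or patients are needed. A mean shift can miss a problem confined to one or two infants; the retained counts cover that.
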